STUDY PROTOCOL

Official Title: *Effect of Menstrual Cycle on Postoperative Sensitivity and Rebound Pain in Posterior Composite Restorations: A Double-Blind Split-Mouth Clinical Study*

Unique Protocol ID: FIRAT-DENTISTRY [name]-001

NCT ID:

Date: 01.09.2022

Principal Investigator: [name], PhD, Assistant Professor

Affiliation: Firat University, Faculty of Dentistry, Department of Restorative Dentistry, Elazig, Turkey

✉@ mail [contact]

📞 [contact]

Study Objectives:

- **Primary Objective:** To evaluate the effect of menstrual cycle phases on postoperative sensitivity (POS) following direct posterior composite restorations.
-
- **Secondary Objective:** To assess whether menstrual cycle phases influence the incidence or severity of rebound pain (RP) after inferior alveolar nerve block (IANB).

Study Design:

- **Type:** Double-blind, split-mouth, randomized clinical trial
- **Study Groups:**
 - **Menstrual Phase Group (MPG):** Restorations performed during **days 1-3** of menstruation.
 - **Ovulatory Phase Group (OPG):** Restorations performed on **days 11-16**, depending on cycle length.
- **Number of Participants:** 35 women, each receiving two restorations
- **Total:** 70 restorations).
- **Masking(Blinding):**
 - The operator performing the restorations and the researcher assessing the outcomes were blinded to menstrual cycle phases.

Eligibility Criteria:

Inclusion Criteria:

- Women aged 18-45 years
- Regular menstrual cycles (26-32 days)
- No hormonal contraceptive use
- Vital posterior mandibular molar teeth requiring restorative treatment
- Good oral and periodontal health

Exclusion Criteria:

- Irregular menstrual cycles or hormonal disorders
- Pregnancy or lactation
- Use of analgesics or anti-inflammatory drugs within 48 hours before treatment
- Severe periodontal disease or need for endodontic treatment

Interventions & Procedures:

- **Anesthesia:** Inferior alveolar nerve block (**IANB**) with articaine hydrochloride with epinephrine (1:100,000)
- **Restorative Material:** Clearfil Universal Bond Quick (Kuraray, Japan) and Clearfil Majesty Posterior (Kuraray, Japan) .
- **Postoperative Sensitivity (POS) Assessment:**
 - VAS (0-10) measured at Day 1, Day 2, and Day 3 after restoration.
- **Rebound Pain (RP) Assessment:**
 - VAS (0-10) measured at Hour 4, Hour 8, and Hour 12 after anesthesia resolution.

Statistical Analysis:

- **Cochran's Q test** for intragroup comparisons
- **McNemar's test** for post-hoc analysis
- **Chi-Square test or Fisher's Exact Test** for intergroup comparisons
- **Bonferroni correction** for multiple comparisons
- **Significance Level:** $p < 0.05$

Ethical Approval:

- Non-Interventional Research Ethics Committee of Firat University
- Reference No: 2022/08-07
- **ClinicalTrials.gov Registration No:** has not been created yet

Date of creation: 01.09.2022

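### The trial is labelled randomised, but the plan does not say what is randomised or how; unless visit order and tooth are randomly assigned, both can be mistaken for a cycle-phase effect.

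*Combined protocol and SAP*

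**What the plan says.** The Study Design section describes a "Double-blind, split-mouth, randomized clinical trial". This is the only mention of randomisation in the document; the official title says "A Double-Blind Split-Mouth Clinical Study", without that word.

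The groups are set by timing. The menstrual group is "Restorations performed during days 1-3 of menstruation"; the ovulatory group is "Restorations performed on days 11-16, depending on cycle length". There are "35 women, each receiving two restorations", giving "70 restorations" in all, so each woman contributes to both groups. The tooth criterion is "Vital posterior mandibular molar teeth requiring restorative treatment".

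On masking: "The operator performing the restorations and the researcher assessing the outcomes were blinded to menstrual cycle phases". The section does not mention sequence generation, concealment, which phase comes first, which molar goes with which phase, or matching of the two cavities. Statistical Analysis lists Cochran's Q and McNemar for comparisons within a group, and chi-square or Fisher between groups. None of these is specified with a term for visit order or tooth.

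**The concern.** Phase is the only exposure under study, and it is a time window that is observed, not allocated. Treating each woman in both phases removes differences between women. It leaves two differences within a woman: one restoration is done at her first visit and the other at her second, and they are in different teeth.

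If first visits fall more often in one phase, any first-visit effect (anxiety, unfamiliarity with the VAS) enters the phase comparison. If the tooth more prone to sensitivity is treated more often in one phase, that enters too. Masking the operator and assessor balances neither. What is at stake is the primary comparison, postoperative sensitivity by phase, and the rebound-pain comparison built on the same visits.

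The word randomised tells a reader that these differences are balanced by design. From this plan nobody could carry out, or check, the allocation that would do so.

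**Working it through.** **The plan's own figure.** 35 women x 2 restorations = 70, which agrees. The document gives no effect size, SD, power or dropout, so no other figure can be reproduced.

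**Bias.** Let e be the period effect (first visit minus second visit, in VAS points) and p the share of women treated menstrual-first. With no true phase effect, the menstrual-minus-ovulatory difference is centred on +e for a menstrual-first woman and on -e for an ovulatory-first woman. Its mean is pe - (1 - p)e = (2p - 1)e. The same algebra applies to tooth: replace p by the share of women whose more sensitive tooth is treated in the menstrual phase, and e by the difference between teeth. The document gives no basis for sizing the tooth effect, so only order is sized here.

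**Inputs.** n = 35 is from the plan. The 5% level is from the plan; two-sided is assumed. Assumed: e = 0.5 to 1.0 VAS points, and a residual SD of the within-woman difference of 2.0 (range 1.5 to 2.5). The test is a paired t test, used for illustration; the plan does not list it.

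**Variance.** When both orders occur, the +e and -e shifts add 4p(1 - p)e² to the variance of the differences. At 18/17 and e = 1.0 this is 4 + 0.999 = 5.0, an observed SD of 2.24. At p = 1 nothing is added. Type I error was therefore simulated with fixed order counts (400,000 trials per setting).

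| Menstrual-first | Bias (e = 0.5; 1.0) | Type I error, SD 2.0 (e = 0.5; 1.0) | Range over SD 1.5-2.5 |
|---|---|---|---|
| 18 of 35 | 0.01; 0.03 | 4.3%; 2.9% | 2.0-4.6% |
| 24 of 35 (p = 0.69) | 0.19; 0.37 | 7.5%; 13.7% | 6.7-18.9% |
| 25 of 35 (p = 0.71) | 0.21; 0.43 | 8.5%; 17.9% | 7.4-25.7% |
| 35 of 35 | 0.50; 1.00 | 30%; 82% | 21-97% |

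The last row can be checked directly: the non-centrality is e√35/2.0 = 1.48 or 2.96, and the non-central t with 34 degrees of freedom gives 0.301 and 0.820. If 2.0 is instead taken as the total SD, so that a mixed order adds nothing to it, the same formula gives 5% at 18/17 and 9-21% at p = 0.7.

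**Where might p lie?** The plan does not say. Suppose enrolment is spread evenly over the cycle, each woman takes the first window to arrive, and the whole of days 11-16 is open. Women enrolled on days 4-16 are then ovulatory-first and all others menstrual-first. Over the eligible cycle lengths this gives p = 13/26 = 0.50, 15/28 = 0.54 and 19/32 = 0.59. The bias at 28 days is 0.04 to 0.07 VAS points, and at 32 days 0.09 to 0.19. If bookings are instead made from the onset of menses, p could approach 1. Both are assumptions.

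**The case against.** The strongest reply is that the plan is a short synopsis and does claim randomisation. Order and tooth are the only things that could be randomised, so the label may refer to them. That stands as far as it goes. A reader might infer that nothing was allocated at random, and might take the omission from the title and the approval by an ethics committee for non-interventional research as support. Neither settles the matter: the document does not describe random allocation, but it does not exclude it.

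A reader might also infer that women are booked menstrual-first because cycle days count from menses, or that the worse tooth is treated first. Neither is in the document. The first-available calculation gives a near-even order with no randomisation at all, so the 30-82% figure describes an extreme and is not a forecast.

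Finally, these type I errors belong to a paired t test on VAS, not to the listed categorical tests. That is correct, and they serve only to show scale. The bias expression depends on no particular test.

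What the reply does not remove is the gap itself. Followed as written, the plan leaves order and tooth to be settled in some unstated way, and it names no analysis that would correct for order.

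**Conclusion.** The concern holds in conditional form. The plan uses the word randomised without saying what is randomised or how, and it does not protect the phase comparison from visit-order or tooth differences. With order close to balanced there is almost no order bias (0.01 to 0.03 VAS points at 18/17), and an unadjusted paired test is slightly conservative. Harm grows with imbalance: about 7-18% type I error at p near 0.7, and 30-82% if all women share one order, in which case phase and visit cannot be separated by any analysis. These figures rest on an assumed period effect of 0.5-1.0 and residual SD of 2.0; p is unknown. The tooth effect has the same form but cannot be sized from the document. This should be corrected. It does not show that the comparison is in fact biased.

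**What to change.** - **Allocation.** At enrolment, allocate each woman from a concealed, computer-generated blocked list to menstrual-first or ovulatory-first, crossed with which of her two molars is treated first. Keep the list from the operator and the assessor. The plan names nobody to hold it or schedule visits, so that role must be added.
- **Wording.** State that order and tooth are randomised, and that phase is not.
- **Analysis.** Replace the between-phase chi-square or Fisher comparison with a paired analysis that includes a first/second-visit term. For VAS, one form is to regress the within-woman difference on order coded +1/-1 and read the phase effect from the intercept; for a binary outcome, conditional logistic regression with a visit term.
- **If order and tooth were not randomised.** Drop the word randomised, tabulate order and tooth by phase, and adjust for period where both orders occur. If only one order occurs, say that phase and visit cannot be separated.

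**Cost.** A randomisation list, a changed between-phase analysis (a visit term cannot be attached to the listed tests), and a wait for some women until their allocated phase window. No extra participants are needed.

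### Cavity depth of each woman's two teeth is not specified to be recorded or used, so tooth differences stay in the phase comparison as avoidable noise

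*Combined protocol and SAP*

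**What the plan says.** Study Design describes a "Double-blind, split-mouth, randomized clinical trial" with "35 women, each receiving two restorations", one in each cycle phase, giving "70 restorations" in all. It does not say how tooth or side is assigned to phase.

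Under Eligibility Criteria, the teeth admitted are "Vital posterior mandibular molar teeth requiring restorative treatment". The other restrictions that bear on the teeth are a general requirement for a healthy mouth and the exclusion of "Severe periodontal disease or need for endodontic treatment". Neither Eligibility Criteria nor Interventions & Procedures mentions cavity depth, cavity class, number of surfaces or lesion size. No rule makes a woman's two teeth comparable.

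The primary objective is "To evaluate the effect of menstrual cycle phases on postoperative sensitivity (POS) following direct posterior composite restorations", assessed as "VAS (0-10) measured at Day 1, Day 2, and Day 3 after restoration".

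Statistical Analysis lists Cochran's Q within each phase, McNemar's test as the post-hoc test, a Bonferroni correction, and the chi-square or Fisher's exact test "for intergroup comparisons". No covariate or stratum is named, and there is no regression model.

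**The concern.** In a split-mouth design each woman is her own control, so her pain threshold and reporting style cancel. Her two teeth are still two different teeth. One may have a shallow cavity and the other a deep one, and the outcome is the sensitivity of the restored tooth. The protocol fixes the jaw, tooth type, adhesive, composite and anaesthetic, but leaves the cavity open.

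If depth affects postoperative sensitivity, two things follow even with perfect randomization. The paired difference is more variable than it need be, and with only 35 pairs one phase may by chance receive more of the deeper cavities. These are one effect seen from two sides: the chance imbalance is already part of the standard error and is not a further error on top of it. If depth is not recorded, a reader cannot see how the cavities fell between the phases, and the analyst cannot recover the lost precision.

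**Working it through.** **The plan's own figure.** 35 × 2 = 70 restorations, as stated. The 35 itself cannot be reproduced, because no power, effect size, SD or event rate is given.

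**Assumed inputs.** None of these is in the documents.
- g, extra VAS points from a deeper cavity: 1.0 to 1.5.
- f, share of women whose two teeth differ in depth (two levels): 0.3 to 0.5.
- SD of the within-woman difference between phases, including the part due to depth: 2.0.

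**Share of paired variance due to depth** = g² × f / SD².
- Low: 1.0² × 0.3 / 4 = 0.075.
- High: 1.5² × 0.5 / 4 = 0.281.

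**Equivalent number of pairs after adjustment** = 35 / (1 − share).
- Low: 35 / 0.925 = 37.8, about 38.
- High: 35 / 0.719 = 48.7, about 49.

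These are upper limits. They treat the depth coefficient as known and the depth category as error-free.

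**Allowing for estimation of the depth coefficient.** Simulating 35 pairs on the same inputs, with teeth assigned to phase at random, gives a standard error about 2 to 3% smaller at the low end and 13 to 14% smaller at the high end. In pairs:
- Low: 35 / 0.98² = 36.4 to 35 / 0.97² = 37.2.
- High: 35 / 0.87² = 46.2 to 35 / 0.86² = 47.3.

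**Chance imbalance under correct randomization**, as a 95% range for the shift in the mean phase difference = ±1.96 × g × √(f / 35).
- Low: 1.96 × 1.0 × √(0.3 / 35) = ±0.18 points.
- High: 1.96 × 1.5 × √(0.5 / 35) = ±0.35 points.

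**The same question on a yes/no outcome**, which is closer to the tests listed. Let D be the number of women whose teeth differ in depth and RD the difference in the risk of sensitivity between deep and shallow cavities. The 95% shift is ±1.96 × (√D / 35) × RD.
- D = 10, RD = 0.10: ±1.8 percentage points.
- D = 18, RD = 0.20: ±4.8 points.
- D = 24, RD = 0.30: ±8.2 points.

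An illustrative simulation used an exact McNemar test on 35 pairs, a phase odds ratio of 4 and a woman-level SD of 1.5 on the logit scale. McNemar is not the plan's between-phase test.

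| Women with teeth of different depth | Power, depth OR 2 | Power, depth OR 4 |
|---|---|---|
| None | 0.53 | 0.52 |
| Half | 0.53 | 0.49 |
| All | 0.51 | 0.46 |

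Under random assignment the type I error stayed at 0.021 to 0.026 throughout.

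**The case against.** The strongest reply is that the trial is described as randomized. If teeth are assigned to phase at random, depth differences cause no systematic error, and the power lost is small: 0 to 3 points if half the women have teeth of different depth, and at most about 6 points if all do. That stands, and it sets the size of this point.

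A reader might infer more, namely that the phase effect is biased. Suppose the deeper tooth is always treated first and 70% of women start in the menstrual phase. The unadjusted bias would be g × f × (2 × 0.7 − 1), that is 1.0 × 0.3 × 0.4 = 0.12 to 1.5 × 0.5 × 0.4 = 0.30 points. The documents do not support this as a finding about depth. They report neither the order of teeth nor the split of starting phases. In that scenario depth acts only as a difference between first and second visit, which a period term absorbs: in simulation the bias falls to zero with period in the model and no depth term. Steering deeper teeth directly to one phase would be a different matter, and the protocol's silence on assignment does not rule it out. That silence is a separate gap with its own remedy, and nothing in the text suggests that steering occurred.

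A reader might also infer that depth was never written down. A protocol this short shows only that recording is not specified; it cannot show what the case records hold.

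Three further objections stand. The effect of depth on sensitivity is an assumption from outside the documents. The exclusion of teeth needing endodontic treatment narrows the range of depth, though it does not equalise the rest. And the plan contains no model to which a covariate could be added, so the gain depends on first adopting a paired analysis.

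**Conclusion.** The point holds as a low-cost improvement in precision. The protocol neither specifies recording cavity depth nor provides an analysis that could use it, so differences between a woman's two teeth remain in the phase comparison as noise and chance imbalance.

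Under the assumed inputs, adjustment makes 35 pairs worth at most about 38 to 49, or roughly 36 to 47 once the cost of estimating the depth coefficient is counted. The gain shrinks if the operator's category misclassifies depth or the VAS is cut to yes/no, and it vanishes if depth has no effect on sensitivity. The omission does not invalidate the comparison, and no bias figure should be attached to it.

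**What to change.** 1. Have the operator, who is blinded to phase, record a depth category (for example shallow, medium or deep) for each tooth at the restoration visit, before any outcome is known.
2. Report the distribution of depth by phase. If cavity class is also recorded, report it descriptively only.
3. Replace the unpaired chi-square or Fisher comparison between phases with a paired model: woman as cluster, with phase, period and depth as terms. If the outcome stays binary, a conditional or mixed logistic model serves the same purpose, with a smaller gain from the depth term.
4. Do not require the two teeth to be matched on depth, which would slow recruitment.

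The depth term costs one case-form field and one degree of freedom (two categories) or two (three categories) among 35 pairs. Recording class would add a second field. The larger change is the move to a paired model, without which the depth field can serve only the descriptive table.

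### POS and RP are collected as 0-10 VAS scores, but every listed test is for unordered categories that the plan does not define, and RP severity has no order-respecting analysis

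*Combined protocol and SAP*

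**What the plan says.** Under Study Objectives, the primary aim is "To evaluate the effect of menstrual cycle phases on postoperative sensitivity (POS) following direct posterior composite restorations". It does not say whether occurrence or severity is meant. The secondary aim is to learn whether cycle phases "influence the incidence or severity of rebound pain (RP"), so severity is an explicit target there.

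Under Interventions & Procedures, POS is "VAS (0-10) measured at Day 1, Day 2, and Day 3 after restoration" and RP is "VAS (0-10) measured at Hour 4, Hour 8, and Hour 12 after anesthesia resolution". No other form of either outcome is described.

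Under Statistical Analysis, the whole test list is "Cochran's Q test" within groups, "McNemar's test" as post-hoc, and "Chi-Square test or Fisher's Exact Test" between groups. A Bonferroni correction with no stated divisor and a 0.05 level complete the section. The combined document contains no cut-off, no severity bands, no RP case definition and no summary measure for the VAS.

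**The concern.** The outcome scale and the tests do not meet. A 0-10 score is ordered, and the listed tests take categories and make no use of order. Someone has to supply a rule that turns scores into categories, and the plan neither states that rule nor says who sets it or when.

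Two things are at stake. First, the POS and RP results depend on an unstated choice that could be made after the scores are seen. Second, the severity question in the secondary objective has no test suited to it: a cut at any pain is nearly blind to a change in how strong the pain is, and an unordered table treats a move from 2 to 3 like a move from 2 to 9.

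**Working it through.** **No planned figure to reproduce.** The protocol gives 35 women and 70 restorations (35 x 2 = 70, which agrees). It gives no power, effect size, SD, correlation or pain prevalence.

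**Step 1: match tests to data. This needs no assumptions.**

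| Listed test | Data it needs | Supplied by the plan? |
|---|---|---|
| Cochran's Q | yes/no at each time | no yes/no rule |
| McNemar | paired yes/no | no yes/no rule |
| Chi-Square/Fisher | categories | no bands; raw integers possible, order ignored |

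If scores are whole numbers, the raw table has 11 values x 2 phases = 22 cells for 70 restorations, or 70/22 = 3.2 per cell on average. That is sparse, and shuffling the score labels would leave the p-value unchanged. No listed test uses the order of the full score.

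**Step 2: illustration of how much the rule matters. All inputs are assumed.** VAS = base + day effect (+0.5, 0, -0.5) + woman N(0, SD 1.4) + visit N(0, SD 1.1) + day N(0, SD 1.0), rounded and clipped to 0-10, with 35 pairs. Three bases (2.5, 0, -1) give 89/50/31% with any pain on Day 1 in the lower-pain phase; triplets below follow that order. A latent shift of 1.0 becomes, after clipping, a realised Day-1 mean difference of about 0.95/0.68/0.50, so prevalence and effect size change together. Tests are at unadjusted 0.05 on Day 1 unless stated.

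- *Cut dependence, Chi-Square/Fisher.* Cuts at >=1 and >=3 disagree (one significant, one not) in 31/35/32% of trials. With an assumed Bonferroni divisor of 3 this falls to about 16/23/20%.
- *Severity-only effect (+1 where pain is present).* McNemar at >=1 detects 2-4%, and at >=3 it detects 40/36/21%. Signed-rank on the scores detects 65/38/25%.
- *Order ignored, four bands (0/1-3/4-6/7-10), both tests unpaired.* For the 1-point shift, Chi-Square has 22/26/23% power and Mann-Whitney 51/45/37%. For the severity-only effect it is 24/13/6% against 44/9/4%, so the loss is not uniform.
- *No true difference, cut picked afterwards from >=1 to >=5.* Chi-Square/Fisher reject in 8/5/4% (12/9/7% at low within-woman correlation, 3/1/1% at high). With the assumed divisor of 3, at the central correlation, this is about 1-2%.

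**Step 3: where a score analysis does worse. Same caveat.**

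- *Incidence-only effect (20 vs 50%, or 50 vs 80%, with any pain).* McNemar at >=1 has 79-88% power. Signed-rank has 52-71% on Day 1. On the 3-day mean it has 52-71% if pain is constant over the days and 85-96% if it varies by day.
- *Shift confined to Day 1.* Signed-rank on the 3-day mean has 20/23/23% power, against 74/66/56% on Day 1 alone.

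**The case against.** Several points on the other side have force.

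- *Analysing pain as yes/no is legitimate.* It is, for incidence, provided the cut is fixed in advance. The defect is that none is.
- *The phase comparison can be run.* Chi-Square/Fisher, the tests assigned to the comparison between phases, do accept integer scores. This stands: it would be wrong to infer that the whole plan is unexecutable. That holds for Cochran's Q and McNemar; for Chi-Square/Fisher the trouble is a sparse, unordered table.
- *Type I error.* A reader might infer that a free choice of cut badly inflates false positives. With the tests planned between phases the figure is about 4-8%, and about 1-2% with an assumed divisor of 3. The larger 16/12/8% comes from McNemar used between phases, whereas the plan lists McNemar as post-hoc.
- *Disagreement in a third of trials has no benchmark.* Fair. In the same model, signed-rank on Day 1 and on Day 3 disagree in 29/35/37% of trials. The percentage shows that the choice matters, not that categorical tests are unusually unstable. The remedy is to name one analysis in advance, whichever kind is chosen.
- *Power.* A reader might infer that yes/no tests always lose power. The documents give no prevalence, SD or effect size, and under some effects the yes/no test wins.
- *Severity is explicit only for RP.* Correct. For POS the gap is an objective that leaves the target open.

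**Conclusion.** The concern holds in a limited form. From the text alone: both outcomes are 0-10 scores at three times; all listed tests are for unordered categories; the yes/no rule required by Cochran's Q and McNemar is absent; RP severity has no order-respecting analysis; and the POS objective does not choose between occurrence and severity. These facts rest on no assumption.

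The size is illustrative only. Under the assumed model, the choice between two plausible cuts changes the significance verdict in about a third of trials at unadjusted 0.05, and in roughly a sixth to a quarter with an assumed divisor of 3. The main harms are an undetermined result and an unanswered severity question, rather than large type I error inflation. The documents do not establish that a score analysis would be more powerful in this trial, nor that the 3-day mean is the only acceptable primary summary. Whether an unpaired test suits a within-woman comparison is a separate matter and is not counted here.

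**What to change.** Before unblinding, amend the Statistical Analysis section as follows.

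1. Analyse RP severity with a paired, order-respecting test: Wilcoxon signed-rank on each woman's MPG-minus-OPG VAS difference. Analyse POS scores the same way. Name one time point or summary in advance for each outcome. The Day 1-3 mean is one option for POS, but it dilutes an effect confined to one day.
2. Keep incidence of POS and RP, with one cut-off fixed in advance. This also makes Cochran's Q and McNemar runnable. State whether the score or the incidence analysis is primary for POS, and word the primary objective to match.
3. Apply the planned Bonferroni correction to any by-day or by-hour tests, and state its divisor.

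The cost is SAP wording; the VAS is already planned. If the score analysis is made primary, the headline becomes a VAS difference rather than a percentage with pain. Power is also lower than for a yes/no test if phase changes only whether pain occurs and the pain persists over the days. The investigators should weigh that when they decide which question about POS they most want answered.

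### Rebound pain is read only at Hours 4, 8 and 12 with no recall period, so on the plain wording incidence is a lower bound and peaks between readings go unrecorded

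*Combined protocol and SAP*

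**What the plan says.** In the combined protocol and SAP, the secondary objective (Study Objectives) reads: "To assess whether menstrual cycle phases influence the incidence or severity of rebound pain (RP) after inferior alveolar nerve block (IANB".

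The only measurement that serves it is under Interventions & Procedures, Rebound Pain Assessment: "VAS (0-10) measured at Hour 4, Hour 8, and Hour 12 after anesthesia resolution". The other pain scale, "VAS (0-10) measured at Day 1, Day 2, and Day 3 after restoration", is assigned to postoperative sensitivity, which is the primary objective.

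The Statistical Analysis section lists "Cochran's Q test" within groups, "McNemar's test" post hoc, and "Chi-Square test or Fisher's Exact Test" between groups. All of these take binary or categorical data.

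The plan does not state:
- whether the patient scores pain now or over a period;
- any reading at resolution of the block or in the next 4 hours;
- a score at which rebound pain counts as present;
- how three readings become one result per restoration.

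**The concern.** Incidence asks whether rebound pain occurred at any time in the window. Severity, as a summary of an episode, asks how bad it became. A score taken at a given hour describes that hour. The clock starts when the anesthesia resolves, yet the first look comes 4 hours later and further looks are 4 hours apart. Pain that comes and goes in a gap is recorded as no pain. Pain that peaks in a gap is recorded below its peak.

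Missed episodes lower the observed incidence in both phases, shrink the absolute difference between them, and so reduce power in a trial of only 35 women. This is a separate matter from the lack of a baseline score: with a baseline in place, the interval between readings would still be unobserved.

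**Working it through.** **The plan's own figure.** Study Design gives "35 women, each receiving two restorations": 35 × 2 = 70, which agrees with the stated "70 restorations". No power, effect size, pain rate or pain duration is stated, so the choice of 35 cannot be re-derived.

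**Inputs from the plan.** Readings at t = 4, 8 and 12 h after resolution; 35 pairs; significance level 0.05 (two-sided assumed).

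**Assumed inputs, not in the documents.** The score is of current pain; there is one continuous episode of length d per affected restoration; onset is uniform over 0–12 h; capture is equal in both phases; a woman's two restorations are independent.

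**Step 1: capture.** An episode is recorded only if it covers 4, 8 or 12 h. For d up to 4 h, each reading catches onsets in the d hours before it, so

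capture = 3d/12 = d/4.

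| Episode length | 1 h | 2 h | 3 h | 4 h or more |
|---|---|---|---|---|
| Captured | 25% | 50% | 75% | 100% |

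Simulation gives the same values. No interval between readings exceeds 4 h, so a continuous episode of at least 4 h that starts in the first 8 h always meets a reading. One that starts between Hours 8 and 12 is still present at Hour 12.

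**Step 2: other onset and duration assumptions.**
- Onset exactly at resolution: an episode is recorded only if it lasts 4 h.
- Onset within the first hour: an episode shorter than 3 h is never recorded; one of 4 h always is.
- Exponential durations with mean 1, 2, 4 and 6 h: capture is 0.245, 0.43, 0.63 and 0.73 with uniform onset, and 0.02, 0.14, 0.37 and 0.51 with onset at resolution.

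**Step 3: power.** With capture c, true incidences p1 and p2 are seen as c·p1 and c·p2. Under independence the two discordant probabilities are c·p1(1 − c·p2) and c·p2(1 − c·p1). For 50% v 20%:
- c = 1: 0.50 × 0.80 = 0.40 and 0.20 × 0.50 = 0.10, so 35 × 0.50 = 17.5 discordant pairs are expected.
- c = 0.5: 0.25 × 0.90 = 0.225 and 0.10 × 0.75 = 0.075, so 35 × 0.30 = 10.5.

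Exact enumeration over the possible tables gives:

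| Capture | Observed incidences | Exact McNemar | Fisher, 35 v 35 |
|---|---|---|---|
| 100% | 50% v 20% | 0.68 | 0.69 |
| 75% | 37.5% v 15% | 0.47 | 0.48 |
| 50% | 25% v 10% | 0.26 | 0.27 |
| 25% | 12.5% v 5% | 0.07 | 0.07 |

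With 40% v 15% instead, McNemar power is 0.55, 0.37, 0.20 and 0.05 at the same four capture levels.

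**Step 4: when a false difference could arise.** Suppose true incidence is 40% in both phases, but episodes last 3 h in one and 1 h in the other. The observed rates are 0.40 × 0.75 = 30% and 0.40 × 0.25 = 10%. Exact McNemar on 35 pairs would then report a difference in incidence 43% of the time.

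**The case against.** **The recall period is unstated, so current pain is an inference.** This stands as a qualification. If patients are asked for their worst pain since the last reading, most of the problem disappears. But the text speaks of a score measured at an hour, and nothing in it points to recall. If recall was intended, the protocol needs to say so. The clock could also be read less literally, as hours from the procedure with every reading falling after resolution. That would shorten the unobserved first interval, so the time origin also needs stating.

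**The readings are not empty.** This stands. A reader might infer that the schedule measures neither incidence nor severity. The objective says incidence or severity, and the readings do give severity at three times and a lower bound on incidence. Long episodes are caught in full.

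**The size of the loss is assumed.** This stands. A reader might take 0.26 as the trial's power. It is one point in a range that runs from no loss to almost no power, and the documents do not say where the trial falls.

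**McNemar is listed for post-hoc use, not for the comparison of phases.** This is correct, but Fisher's test, which the plan does list for that comparison, loses power to almost the same degree.

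**Both phases share one schedule.** This stands. A reader might infer that the secondary question will be answered wrongly. The documents do not support that: step 4 needs phase to change the duration or timing of pain, and they offer no evidence on either. Such an effect would also be a real effect of phase on rebound pain, mislabelled as incidence.

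**Conclusion.** The point holds on the plain wording. Three scores of current pain, the first 4 hours after resolution, under-count rebound pain that starts and ends within a gap, and they do not record peaks between readings. The default consequence is under-ascertainment and lost power in both phases; a false difference in incidence is conditional on phase altering duration or timing.

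The mechanism follows from the schedule once the score is taken as current pain. Its size does not: under the stated assumptions capture runs from 25% to 100% for episodes of 1 to 4 hours, and power for 50% v 20% from about 0.07 to 0.68. The plan should be changed, with the weight due to a secondary objective, because the remedy is cheap and improves the measurement itself.

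**What to change.** Keep the three contacts. At each one, also ask for the worst pain in the treated area since the last reading, scored 0–10; at Hour 4, ask for the worst since numbness ended. State the recall period of every score and confirm that the hours run from resolution.

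Define two endpoints per restoration: rebound pain severity is the highest of the three worst-pain scores, and rebound pain incidence is that maximum reaching a cut-off fixed before any data are seen. Keep the spot scores as descriptive data.

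If the answers are accurate, the three recall periods cover the whole 12 hours and an episode of any length is counted. The cost is one extra diary or telephone question per contact and a short definition in the protocol. The downside is reliance on recall over up to 4 hours.
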